11.5. Efficacy Analyses

The primary and secondary endpoints will be analyzed using the Full Analysis Set (FAS). Other important statistical considerations such as sensitivity analyses and subgroup analyses will be described in the SAP.

The primary endpoint of the study is the change from Baseline in IMR measured immediately after PCI. The primary PD analysis will be analyzed using ANCOVA with a model that includes treatment group and randomization stratification factor as factors and Baseline IMR as a covariate. Least square means, standard errors (SEs), and 95% CIs for the treatments and their difference will be presented together with their p-values.

11.6. Study Endpoints

The following definitions will be used to assess efficacy outcomes:

11.6.1. Primary Endpoint

- Change in IMR from Baseline to Post-PCI

11.6.2. Secondary Endpoints

- Change from Baseline to Post-PCI for the following assessments:
 - Coronary physiology indices (CFR, FFR)

- Angiographic measures (cTFC, TFG, TMPG)
- Myocardial injury markers (CK, CK-MB, cTn)

Note: Post-PCI measure for CK, CK-MB, and cTn, is collected 4 to 6 hours after completion of the PCI procedure and not immediately after completion of the procedure.

- The incidence of procedural myocardial injury defined as: Elevation of cTn values > 99th percentile upper reference limit (URL) in subjects with normal Baseline values (\leq 99th percentile URL) or elevation of cTn by > 20% of the Baseline value in subjects with elevated cTn levels (> 99th percentile URL)
- Concentration of temanogrel and active metabolites AR295980 and AR295981 prior to PCI and at selected post-PCI timepoints until discharge
- Safety and tolerability of temanogrel

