The primary and secondary endpoints will be analyzed using the Full Analysis Set (FAS) and safety endpoints will be performed using the Safety Set. Other important statistical considerations, such as sensitivity analyses, and subgroup analyses will be described in the Statistical Analysis Plan (SAP).

The primary endpoint of the study is the change from Baseline in IMR measured immediately after PCI. The primary PD analysis will be analyzed using analysis of covariance (ANCOVA) with a model that includes treatment group and randomization stratification factor as factors and Baseline IMR as a covariate. Least square means, standard errors (SEs), and 95% CIs for the treatments and their difference will be presented together with their p-values.

Unless otherwise specified, secondary continuous endpoints will be analyzed using ANCOVA with a model that includes treatment group and randomization stratification factor as factors and Baseline IMR value and Baseline values as covariates. Least square means, SEs, and 95% CIs for the treatments and their difference will be presented together with their p-values.

Proportion-based secondary endpoints will be analyzed in the FAS using the Cochran-Mantel-Haenszel method adjusted for randomization stratification factor. The number and percentage of subjects achieving the goal and the difference in proportion between treatment groups achieving the goal, along with p-value and the 95% CIs will be

reported. The odds ratio relative to placebo and percentage of difference from placebo will be presented together with corresponding 95% CIs and the p-values.

Pairwise comparisons of each temanogrel treatment group compared to placebo will be conducted. In addition, analyses of the pooled temanogrel treatment groups compared to placebo will be conducted.

Where statistical assumptions (eg, normality, proportional odds) are not met, alternative approaches will be evaluated (eg, non-parametric analysis, log transformation).

Details regarding the statistical analyses will be provided in the SAP.

Pharmacokinetic analysis:

The PK analysis will be conducted using model independent methods and based on plasma concentrations of temanogrel and its metabolites from subjects who have received temanogrel and have evaluable plasma concentration versus time profiles. The Pharmacokinetic Set will be used to analyze plasma concentrations. Detailed PK analysis procedures will be provided in the SAP.

Safety analysis:

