Stage A is an ascending single dose study planned to consist of 2 cohorts. After treatment of each cohort in Stage A, a safety/tolerability assessment will be conducted by the Data and Safety Monitoring Board (DSMB). Following the safety review of the first cohort in Stage A, the DSMB will recommend whether dose escalation to the next planned dose level in Stage A should occur; the DSMB may also recommend evaluation of an alternative dose in the second cohort in Stage A. Following the safety review of the second cohort in Stage A, the DSMB will recommend whether progression to Stage B should occur; the DSMB may also recommend evaluation of an alternative dose in an additional third dose cohort in Stage A prior to progression to Stage B. After conduct of the final cohort and safety review of Stage A, Stage B may begin. Stage B is a parallel treatment group study planned to consist of a placebo group and 2 active treatment groups (temanogrel doses selected based on safety and tolerability data in Stage A). In Stage B, enrollment will consist of no more than 25% elective PCI subjects and randomization will be stratified by subject type (elective PCI or PCI for non-ST-elevation myocardial infarction [NSTEMI]/unstable angina [UA]).

[figure not shown]
Subjects should be treated with aspirin and an oral P2Y₁₂ inhibitor (ie, DAPT) per site standard of care; however, subjects in Stage A may only be treated with clopidogrel as the P2Y₁₂ inhibitor DAPT component and may not be treated with prasugrel or ticagrelor until after the subject has completed study participation.

Figure 1: Schematic Diagram of Study Design

Note: Stage A is an ascending single dose study including 2 planned cohorts with an optional third cohort. After completion of Stage A, 2 temanogrel doses will be selected for evaluation in Stage B which will consist of 3 parallel treatment groups (2 temanogrel doses and placebo). Dose escalation procedures in Stage A are described in Section 10.11 and procedures for transitioning from Stage A to Stage B are described in Section 11.11.

Figure 2: Subject Flow of Events

^a Diagnostic angiography including confirmation of lesion-related eligibility can be performed prior to randomization at Check-in or within 60 days prior to Day 1.

^b Can be performed as part of eligibility confirmation/confirmation of suitability for PCI per institutional standards prior to randomization at Check-in.

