4. STUDY POPULATION

4.1. Inclusion Criteria

Subjects must meet ALL of the following inclusion criteria to be eligible for enrollment into the study:

1. Stable angina patients suitable for elective PCI or patients suitable for PCI for diagnosis of NSTEMI/UA. NSTEMI/UA patients are to be consistently hemodynamically stable until the time of PCI and have a thrombolysis in myocardial infarction (TIMI) flow Grade (TFG) 2 or 3 on the diagnostic angiography
2. Target lesions for PCI must appear suitable for stenting as confirmed on the diagnostic angiography. Acceptable lesions cannot be in the left main artery or in a vein or arterial graft, or be a chronic total occlusion or in-stent restenosis. Two or more sequential lesions may be treated in the same artery, as long as they are treated in the same session and at least one of the lesions meets inclusion criteria
 - For elective PCI patients and non-urgent NSTEMI/UA patients (PCI > 12 hours after diagnosis), the lesion must be located in a ≥ 2.75 mm diameter coronary artery; the lesion must also be ≥ 18 mm long and require the use of one or more stents that in total must be ≥ 20 mm long.
 - For NSTEMI patients treated with PCI urgently (within 12 hours after diagnosis), the coronary artery diameter of the culprit lesion must be ≥ 2.75 mm.
3. 30 to 80 years of age, inclusive
4. Female subjects must not be lactating at the time of Screening
5. Females must meet criterion a and males must meet criterion b to qualify for the study:
 - a. Females must not be of childbearing potential by one of the following:
 - Postmenopausal, defined as no menses for 12 months without an alternative medical cause
 - Permanent sterilization procedure, such as hysterectomy, bilateral salpingectomy, or bilateral oophorectomy
 - b. Males with pregnant or non-pregnant female partners of childbearing potential must agree to using a condom during treatment and for 90 days following treatment
6. Body mass index 18.0 to 40.0 kg/m², inclusive
7. Willing to participate in the study and provide written informed consent

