11. PLANNED STATISTICAL METHODS

11.1. General Considerations

Details regarding the statistical analyses will be provided in a Statistical Analysis Plan (SAP), which will be finalized prior to study database lock (unblinding).

Continuous variables will be summarized using the number of observations (n), mean, standard deviation (SD), median, minimum, and maximum. Categorical variables will be summarized using frequency counts and percentages.

Unless otherwise specified, continuous endpoints will be analyzed using analysis of covariance (ANCOVA) with a model that includes treatment group and randomization stratification factor as factors and Baseline IMR value and Baseline value as covariates. Least square means, standard errors (SEs), and 95% confidence intervals (CIs) for the treatments and their difference will be presented together with their p-value.

Proportion-based endpoints will be analyzed by either the Cochran-Mantel-Haenszel method adjusting for randomization stratification factor. The number and percentage of subjects achieving the goal and the difference in proportion between treatment groups achieving the goal, along with p-value and the 95% CIs will be reported. The odds ratio relative to placebo and percentage of difference from placebo will be presented together with corresponding 95% CIs and the p-value.

Pairwise comparisons of each temanogrel treatment group compared to placebo will be conducted. In addition, analyses of the pooled temanogrel treatment groups compared to placebo will be conducted.

Where statistical assumptions (eg, normality, proportional odds) are not met, alternative approaches will be evaluated (eg, non-parametric analysis, log transformation).

Efficacy data will be analyzed by randomized treatment, while safety data will be analyzed by actual treatment received.

All secondary and exploratory analyses will be interpreted in an exploratory manner.

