11.7. Subgroup Analysis

- Sex (male, female)
- Race (white, non-white)
- Age (\leq or $>$ median)
- Baseline IMR (\leq or $>$ median)
- Subject type (elective PCI or PCI for NSTEMI/UA)
- Lesion length (\leq or $>$ median)
- P2Y₁₂ inhibitor exposure (ticagrelor, prasugrel, clopidogrel)
- Time of P2Y₁₂ administration (long-term or procedure loading dose)

Details of the subgroup analyses will be provided in the SAP.

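### The procedural-injury endpoint changes its event rule with Baseline troponin, but the planned CMH test does not stratify on Baseline troponin

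*Combined protocol and SAP*

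**What the plan says.** Section 11.6.2 and the Synopsis define one binary endpoint by two rules. A subject with Baseline cTn at or below the 99th percentile URL is an event if a later value exceeds the URL. For a subject already above it, the rule is "elevation of cTn by > 20% of the Baseline value in subjects with elevated cTn levels".

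The Synopsis gives the analysis: "Proportion-based secondary endpoints will be analyzed in the FAS using the Cochran-Mantel-Haenszel method adjusted for randomization stratification factor". Section 11.1 repeats it: "Proportion-based endpoints will be analyzed by either the Cochran-Mantel-Haenszel method adjusting for randomization stratification factor". The factor is set in Section 3.1: "enrollment will consist of no more than 25% elective PCI subjects and randomization will be stratified by subject type". It has two levels, elective PCI and PCI for NSTEMI/UA.

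Entry is by diagnosis ("Stable angina patients suitable for elective PCI or patients suitable for PCI for diagnosis of NSTEMI/UA"), and no criterion in Sections 4.1 or 4.2 sets a Baseline cTn value. Section 11.7 lists eight subgroup factors; Baseline cTn status is not one of them.

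Continuous endpoints are treated differently. Their ANCOVA includes "treatment group and randomization stratification factor as factors and Baseline IMR value and Baseline value as covariates".

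Section 11.5 leaves room for later detail: "Other important statistical considerations such as sensitivity analyses and subgroup analyses will be described in the SAP". The October 2022 Note to File records the SAP as draft v0.3, which is not among the documents.

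**The concern.** The binary endpoint is the one outcome whose definition depends on the Baseline value, yet it is the one analysed without a Baseline term. Subject type is only a partial proxy for Baseline cTn status, because subjects with normal and with elevated troponin can sit together in the NSTEMI/UA level.

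If the two rules produce different event rates, Baseline status is prognostic for the outcome by construction. Leaving it out of the CMH strata costs precision and lets a chance imbalance between small arms feed into the estimated difference. The pooled odds ratio would also average over two kinds of event with no display of either.

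The primary IMR analysis and the continuous cTn change, which is Baseline-adjusted, are not affected.

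**Working it through.** **The plan's own figures.** None is given for procedural injury. The only calculated figure is for the primary endpoint: 30 per arm, difference 3, SD 3.5, two-sided 0.05. The exact noncentral t power is 90.4%, which agrees with the stated 90% or more but has no bearing on this endpoint.

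**Stratum size (document figures).**
- Elective: 0.25 × 87 = 21.75, so at most 21, or 21/3 = 7 per arm.
- NSTEMI/UA: 87 − 21 = 66 at least, or 66/3 = 22 per arm; 66/87 = 75.9%.

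**What an imbalance does.** Shift in the event difference within the stratum = imbalance in the elevated share × difference between the two rules' event rates. At a 20-point imbalance:
- rates 60% and 20%: 0.20 × 40 = 8 points
- rates 50% and 30%: 0.20 × 20 = 4 points
- equal rates: 0

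**Simulation.** One temanogrel arm against placebo, 29 vs 29 (7 elective + 22 NSTEMI/UA per arm), 50,000 trials per scenario. The test is the CMH chi-square without continuity correction, two-sided 0.05:

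X² = [Σ(aₕ − n₁ₕmₕ/Nₕ)]² / Σ[n₁ₕn₀ₕmₕ(Nₕ − mₕ)/(Nₕ²(Nₕ − 1))]

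Here aₕ is events on temanogrel, mₕ total events, n₁ₕ and n₀ₕ the arm sizes and Nₕ the total in stratum h. The planned version has two strata. The alternative has three: elective, NSTEMI/UA ≤ URL, NSTEMI/UA > URL.

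Assumed, because the documents give none of it: elevated Baseline in 10% of elective and 40, 60 or 80% of NSTEMI/UA subjects; the placebo event rates in the table; odds ratio 1 for type I error and 0.25 for power, with 0.5 as a check.

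Results at 60% elevated, planned → three strata:

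| Placebo event rate, ≤ URL / > URL | Power, OR 0.25 | Power, OR 0.5 | Type I error when arms differ by ≥ 5 in Baseline status |
|---|---|---|---|
| 50/50 | 67.3 → 67.1 | 24.0 → 24.2 | see below |
| 60/40 | 65.7 → 66.2 | 22.9 → 23.8 | 5.6 → 5.0 |
| 70/30 | 57.7 → 61.9 | 19.0 → 21.3 | 8.1 → 5.1 |
| 30/60 | 59.4 → 61.5 | 20.3 → 21.7 | 6.8 → 5.3 |
| 80/20 | 42.5 → 52.2 | 13.4 → 17.1 | 11.7 → 5.0 |

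Over all three elevated shares:
- Overall type I error: planned 4.6-4.8%, three strata 4.8-5.1%.
- Power change at odds ratio 0.25: −0.4 to −0.2 points with equal rates; +0.1 to +4.3 when rates differ by 20-40 points; +5.9 to +10.1 at 80/20.
- An imbalance of 5 or more subjects occurs in 11.5-19.1% of trials. In those trials the planned test's type I error is 5.3-8.4% for rate differences of 20-40 points and 11.7-13.7% at 80/20, against 4.6-5.8% with three strata.
- With equal rates, imbalance does no harm. A separate run at 40/40 with half of NSTEMI/UA elevated gave 4.8% planned and 5.0% with three strata when the elevated shares differed by 20 points or more.

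Repeat runs with 200,000 trials per scenario agree within simulation error.

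**Why not cross both factors fully.** With 7 elective subjects per arm and a 10% elevated share, the chance that the elective/elevated cell is empty in at least one of two arms is 1 − (1 − 0.9⁷)² = 0.73. It is 0.91 at a 5% share and 0.38 at 20%.

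**Sampling window.** The endpoint note allows 4 to 6 hours after PCI. The Appendix 1 column is 6 h ± 2 h, that is 4 to 8 h. Hours 6 to 8 meet the schedule but fall outside the note.

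**The case against.** Adjusting a CMH test for the randomization factor is conventional and valid, and overall type I error is close to nominal. On this view the point is only that another covariate might help, which is true of any small trial. The conditional error rates come from selecting trials with an imbalance, and any unadjusted prognostic factor would show the same pattern. Everything beyond 66 of 87 is assumed. An odds ratio of 0.25 is a very large effect; at 0.5 the gain is about 0-2 points outside the 80/20 case, on a test with power near 20%. The three-stratum remedy still leaves both rules mixed among elective subjects, and the planned pooled temanogrel comparison was not simulated. The SAP might have dealt with this. Development has stopped, and the replacement report lists no incidence table, although its subject-level marker listing would let a reader split the data by Baseline status.

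Most of this stands as a limit on size. It does not remove the gap. Baseline cTn is not just any covariate, because it selects which event rule applies, and the plan already adjusts for Baseline in every continuous endpoint. Leaving elective subjects in one stratum is a deliberate trade against empty cells. One further limit applies: both rules rest on a single Baseline sample, and troponin from the index event can cross either threshold. Splitting on Baseline status therefore does not separate procedural injury from index-event injury.

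**Conclusion.** The concern holds, as a minor one. On the protocol text, two event rules can operate inside one CMH stratum of at least 66 of 87 Stage B subjects, and nothing in the planned binary analysis accounts for which rule applied. There is no bias on average and no effect on the primary endpoint. The loss is a few points of power at most unless the two rules' event rates are very far apart, plus exposure to chance imbalance. How far the rules mix in practice is unknown, because the documents give neither the share with elevated Baseline nor any event rate. The count of 66 assumes exactly 87 subjects with the elective cap reached; fewer elective subjects would enlarge the stratum. With none, the power change is +0.2 to +6.5 points, or +9.0 to +13.0 at 80/20. The finding concerns the planned analysis as the protocol states it; the SAP draft could not be checked.

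**What to change.** 1. Name the single assay, hs-cTnT or cTnI, that defines both the endpoint and Baseline status. Section 10.4.3.3 collects both, and a subject could be normal on one and elevated on the other.
2. Stratify the CMH by subject type and Baseline cTn status, with a prespecified sparse-cell rule that keeps elective as one stratum: elective; NSTEMI/UA ≤ URL; NSTEMI/UA > URL.
3. Tabulate injury incidence by arm within each Baseline group, descriptively. Leave the event definition as written.
4. Separately, reconcile the 4 to 6 hour note in the Synopsis and Section 11.6.2 with the 6 h (± 2 h) column in Appendix 1.

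The cost is protocol and SAP wording. Appendix 1 already schedules the Baseline sample before study treatment, so it is a legitimate stratum. No further subject becomes unassessable, because neither event rule can be applied without a Baseline value. The downside is up to 0.4 point of power if the two rules have equal event rates (0.8 point with four fully crossed strata), and small cells in the descriptive table.

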11.6.3. Exploratory Endpoints

- The relationship between temanogrel/active metabolite exposure and change in IMR from Baseline to Post-PCI (and potentially other PD assessments)
- The relationship between coronary physiology indices/angiographic measures and peripheral serotonin concentrations at Baseline and Post-PCI
- The relationship between coronary physiology indices/angiographic measures and coronary artery serotonin concentration (obtained on blood samples drawn from the coronary ostium and from coronary artery distal to the lesion) Post-PCI
- The relationship between the level of P2Y₁₂ platelet inhibition and peripheral/coronary artery (obtained on blood samples drawn from the coronary ostium and from coronary artery distal to the lesion) serotonin concentrations
- Change in IMR (and potentially other coronary physiology indices) from Baseline to Pre-PCI
- Change in QCA from Baseline to Post-PCI
- Change in the following markers of inflammation from Baseline to post-procedure:
 - hs-CRP, PTX-3
 - Cytokines (IL-1, IL-6, IL-8, IL-10, and TNF- α)

11.6.4. Pharmacokinetic Analysis

The PK analysis will be conducted using model independent methods and based on plasma concentrations of temanogrel and its metabolites from subjects who have received temanogrel. C_{max} and potentially additional pharmacokinetic parameters, will be derived from subjects with evaluable plasma concentration versus time profiles.

Individual plasma concentrations of temanogrel and metabolites will be listed for each subject using the actual sampling time and dose level. The Pharmacokinetic Set will be used to analyze plasma concentrations. Mean, SD, CV (%), median, minimum, and maximum values will be

summarized descriptively as appropriate per dose level. Individual subject plasma concentration versus time profiles of temanogrel and its metabolites will be plotted on both a linear and a semilogarithmic scale for each dose level. Mean values, as appropriate, will also be presented graphically for each dose level.

Detailed PK analysis procedures of temanogrel and its metabolites will be provided in the SAP.

11.6.5. Pharmacokinetic/Pharmacodynamic Relationship

Relationships will be explored between selected plasma exposure measures (to be determined) of selected analytes (temanogrel, its active metabolites, and/or all analytes combined) and selected PD measures (eg, change from Baseline to Post-PCI in IMR and/or other cardiac physiology indices, angiographic measures, markers of myocardial injury/infarction, or markers of inflammation).

Detailed description of the exploratory PK/PD analyses will be provided in the SAP.

11.7. Subgroup Analysis

- Sex (male, female)
- Race (white, non-white)
- Age (\leq or $>$ median)
- Baseline IMR (\leq or $>$ median)
- Subject type (elective PCI or PCI for NSTEMI/UA)
- Lesion length (\leq or $>$ median)
- P2Y₁₂ inhibitor exposure (ticagrelor, prasugrel, clopidogrel)
- Time of P2Y₁₂ administration (long-term or procedure loading dose)

Details of the subgroup analyses will be provided in the SAP.

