Serotonin plasma concentrations will be measured in peripheral blood (from blood samples drawn by venipuncture or indwelling catheter) and coronary artery (from blood samples drawn from the coronary ostium and from coronary artery distal to the lesion) to assess the relationship between serotonin release and change in IMR (and potentially other coronary physiology and/or angiographic measures), and the effect of temanogrel in this setting. Considering that serotonin release requires activation of platelets, the extent of platelet inhibition due to DAPT background therapy (including P2Y₁₂ inhibitors) will also be assessed. The aim of these assessments is to evaluate the relevance of the serotonin pathway in this setting and to establish the proof-of-mechanism for temanogrel.

Bleeding complications have been associated with an increased risk of subsequent adverse outcomes in patients undergoing PCI. Therefore, an important safety measure throughout this study is the monitoring of all adverse events including bleeding events which will be classified using the Bleeding Academic Research Consortium (BARC) bleeding criteria (Mehran 2011), a universal standardized criteria of bleeding severity.

This study has been designed as a randomized, double-blind, placebo-controlled study to reduce bias and account for placebo effect in the evaluation of the safety and PD of IV temanogrel.

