6.7.1. Required Concomitant Therapy

Subjects should be treated with aspirin and an oral P2Y₁₂ inhibitor (ie, DAPT) per standard institutional practices. Subjects may enter the study while on background therapy of DAPT; if subjects are not on background DAPT therapy on the day of their procedure, DAPT treatment should be started prior to the start or during the PCI procedure, per standard institutional practices and according to the American College of Cardiology clinical practice guidelines (Levine 2016) or the European Society of Cardiology (ESC) guidelines (Neumann 2019). Subjects in Stage A may only be treated with clopidogrel as the P2Y₁₂ inhibitor DAPT component and may not be treated with prasugrel or ticagrelor until after the subject has completed the study participation. Subjects in Stage B can be treated with any P2Y₁₂ inhibitor as part of DAPT. Details of DAPT treatment including the time of administration and exact dose of aspirin and P2Y₁₂ inhibitors will be captured in the eCRF.

As part of the IMR assessment, 140 µg/kg/min of adenosine will be infused intravenously for each IMR assessment.

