11.2. Determination of Sample Size

This study is planned to randomize, treat, and complete safety, tolerability, PK, and PD assessments in approximately 99 subjects (12 in Stage A, 87 in Stage B).

It is assumed that the primary endpoint, which is the change from Baseline in IMR measured immediately after PCI, is normally distributed with a mean of 6 and SD of 3.5. Assuming a 1:1:1 randomization, 90 evaluable subjects (30 subjects in each of the 2 temanogrel treatment groups and placebo) is sufficient to achieve at least 90% power to detect a treatment effect of 3 (a clinically significant reduction of 50% from placebo) between each of the temanogrel treatment groups and placebo by a 2-sample t-test using a 2-sided significance level of 0.05.

The primary endpoint analysis will be based on pooled data from subjects in Stage A and Stage B.

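### The P2Y12 agent subgroup is not tied to status at randomisation, Baseline VerifyNow is not used as an effect modifier, and three continuous modifiers are cut at the median

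*Combined protocol and SAP*

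**What the plan says.** Section 11.7 lists eight subgroups. Two concern P2Y12 therapy: agent, given as "inhibitor exposure (ticagrelor, prasugrel, clopidogrel"), and timing, given as "administration (long-term or procedure loading dose"). Three continuous variables (age, Baseline IMR, lesion length) are divided at the median. The section names no subgroup model or interaction test and leaves the details to the SAP.

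Section 6.7.1 covers subjects who arrive without background therapy: "DAPT treatment should be started prior to the start or during the PCI procedure", following institutional practice and guidelines. Stage A allows clopidogrel only; Stage B allows any P2Y12 agent. Times and doses go into the eCRF.

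Sections 9.2 and 10.9 fix the order of events: randomisation, study treatment, Pre-PCI physiology, PCI, then Post-PCI physiology within 15 minutes of the end of PCI.

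Section 3.2 says that "the extent of platelet inhibition due to DAPT background therapy" will be assessed as part of the proof of mechanism. Appendix 1 schedules VerifyNow at Baseline (before study treatment) and Post-PCI. Section 11.6.3 relates P2Y12 inhibition to serotonin concentrations only.

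**The concern.** A subgroup variable should be fixed before treatment can influence it. For a subject first given an oral P2Y12 inhibitor during PCI, the agent is chosen after study drug has been given and after the Pre-PCI physiology has been measured. Blinding limits deliberate selection, but it does not turn a post-dosing variable into a baseline one.

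The agent label also pools two different states. A subject on long-term ticagrelor and one given a first dose during PCI both count as ticagrelor, although IMR is read within minutes of the end of PCI. The documents give no onset times, so weaker inhibition at that reading is an inference. What is certain is that the agent label cannot tell the two apart.

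At stake is an exploratory question of mechanism: does the effect of temanogrel depend on background platelet inhibition? The direct pre-dose measure of that inhibition is collected, but no listed analysis uses it as a modifier of the treatment effect.

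Cutting continuous modifiers at the median is a separate issue. It discards information that a trial of about 99 subjects can ill afford if modification is to be tested.

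**Working it through.** **1. The plan's own figure.** Inputs from section 11.2: the primary endpoint "is normally distributed with a mean of 6 and SD of 3.5"; a difference of 3; 30 per arm; tested "by a 2-sample t-test using a 2-sided significance level of 0.05".

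- Standard error = 3.5 × √(2/30) = 0.904, and 3/0.904 = 3.32.
- Power is 90.4% by noncentral t on 58 degrees of freedom, and 91.3% by the normal approximation.

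The stated 90% reproduces. The plan gives no figure for subgroup or interaction analyses.

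**2. Which P2Y12 label can change after dosing.**

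- *Agent.* For a subject already on therapy it is known before randomisation. For a subject without therapy it may be set during PCI, at step 9 of the order in section 10.9; randomisation is step 2 and dosing step 6. Section 11.7 does not exclude this.
- *Timing.* Long-term use is a fact that predates randomisation, and the loading group is essentially everyone else. The clock time of a load can move; the label mostly cannot. Only reloads and switches are unclear.

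**3. Size of the bias in the agent subgroups.** The documents give neither the share loaded during PCI nor any link between coronary flow and choice of oral agent. Both are assumptions: 25% to 50% loaded during PCI; choice tied to IMR change with a log-odds of 0.5 to 1 per SD; true effect −3 in everyone; 2,000,000 simulated subjects.

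- Whole agent subgroups, as planned: −2.8 to −3.0, a bias of 0 to 0.2.
- Late-loaded subjects taken alone: −2.5 to −2.9. Section 11.7 does not list agent-by-late-load cells.

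For scale, take pooled drug against placebo at 2:1 with SD 3.5 in a subgroup of m subjects. The standard error is 3.5 × √(1/(2m/3) + 1/(m/3)) = 3.5 × √(4.5/m). That is 1.05 for m = 50 and 1.48 for m = 25. A bias of 0.2 is at most about 0.2 of a standard error.

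**4. Information lost by a median split.** For a linear interaction, the share kept is the squared correlation between the covariate and its above-median indicator. For a normal covariate this is 2/π = 0.637, so 36.3% is lost. The documents give no covariate distributions. Other shapes, by simulation:

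| Covariate shape | Lost |
|---|---|
| Uniform | 25% |
| Log-normal, log-SD 0.3 | 41% |
| Log-normal, log-SD 0.5 | 48% |
| Exponential | 52% |
| Log-normal, log-SD 0.7 | 58% |

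**5. Power of an interaction test, if one is done.** Simulated with a normal covariate, residual SD 3.5 and two-sided 0.05:

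| Comparison | Change in effect per covariate SD | Median split | Continuous |
|---|---|---|---|
| Pooled 66 v 33 (99 enrolled) | 2 | 0.52 | 0.73 |
| Pooled 66 v 33 | 1.5 | 0.33 | 0.48 |
| Pooled 66 v 33 | 1 | 0.19 | 0.26 |
| Pooled 60 v 30 (90 evaluable) | 2 | 0.48 | 0.68 |
| One dose 33 v 33 | 2 | 0.41 | 0.60 |

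A slope of 2 per SD is a large modification. Between the two halves of a normal covariate it means 2 × 2 × √(2/π) = 3.2 IMR units, more than the whole assumed effect of 3.

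**The case against.** The strongest reply has four parts.

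*The P2Y12 labels are largely baseline facts.* This stands for timing, as step 2 shows. A reader might infer that both P2Y12 subgroups are post-randomisation variables. The documents support that only for agent, and only for subjects not already on therapy.

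*Nothing shows that oral agent choice follows coronary flow.* This also stands. Section 6.7.1 ties the choice to institutional practice and guidelines. The bail-out measures named for no reflow (sections 5.1 and 10.3) are cangrelor, glycoprotein IIb/IIIa inhibitors and prolonged anticoagulation, none of them an oral agent in the section 11.7 list. A reader might infer material selection bias; step 3 shows little even when the mechanism is assumed.

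*P2Y12 inhibition is already measured directly, and restricting Stage A to clopidogrel is deliberate design.* Both are true. But the measurement is linked only to serotonin, so the use of VerifyNow as a treatment-effect modifier is still missing. The Stage A restriction covers 12 of 99 planned subjects and is not an error; it only means that agent and stage overlap in part.

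*Median splits may be for description only, since no interaction test is named.* This is fair, and it makes the loss conditional. A reader might infer that the subgroup plan as a whole throws away a third of the interaction information. That overreaches: it concerns 3 of 8 subgroups, and the figure needs a normal covariate, a linear interaction and a test that section 11.7 does not specify. For weak modification, power is poor under either approach.

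**Conclusion.** The point holds as a modest improvement to exploratory analyses. The agent subgroup should be tied to status at randomisation, because as written it can include post-dosing choices and mixes subjects loaded during PCI with those already treated. The number affected is unknown, and the likely bias in the planned subgroups is small (0 to 0.2 IMR units under assumptions the documents do not supply). Misclassification and the unused Baseline VerifyNow value carry the argument. The timing subgroup needs only a clarification for reloads and switches.

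For age, Baseline IMR and lesion length, the median split costs about 36% of the interaction information under normality and linearity, with 25% to 58% over the other shapes tried. This matters only if modification is tested.

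The practical consequence is limited. Section 11.1 treats everything beyond the primary analysis as exploratory. The Note to File of 07 October 2022 records that enrolment was terminated and the SAP stayed in draft, and its list of final-report contents shows no subgroup table. None of this touches the primary analysis or the sample size.

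**What to change.** In section 11.7 and the SAP:

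1. Define the P2Y12 subgroups by agent and status at randomisation (which agent is on board, or none). Do not classify subjects by a drug first given after study treatment. State how reloads and switches are handled in the long-term versus loading-dose label.
2. Add Baseline VerifyNow as a continuous modifier, through a treatment-by-VerifyNow term in the IMR model. It is drawn before study treatment, so treatment cannot affect it.
3. Analyse age, Baseline IMR and lesion length as treatment-by-continuous-covariate interactions. Report estimates with confidence intervals, and keep the median splits for display.

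The cost is wording and programming only. VerifyNow, antiplatelet times and doses, and the baseline values are already collected, and no clinical procedure changes. The downside is that a continuous interaction assumes a roughly linear trend; a plot of effect against the covariate, or the displayed split, gives a simple check.
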